Erondu et al. from Janssen Company informed that in CANVAS study (CANAGLIFLOZIN Cardiovascular Assessment Study) until May 2015, there have been 15 cases of diabetic ketoacidosis associated with canagliflozin from 17,596 participants (incidence rate of 0.5, 0.8 and 0.2 per 1,000 patients/year for canagliflozin at 100 mg, 300 mg and comparator, respectively) [83]. Meanwhile, AstraZeneca Company has reported a frequency of 0.1% of possible events related to dapagliflozin from DECLARE's study (Dapagliflozin Effect on Cardiovascular Events) and Boehringer has reported the same incidence in the study EMPA-REG that includes 7,000 patients in treatment with empagliflozine [81]. From these data, canagliflozin is the drug most associated with ketoacidosis, however up to 50% of the reported cases are patients with T1D, in whom the use of iSGLT2 is not authorized.

Regarding euglycemic ketoacidosis' pathophysiological mechanism, it has been observed that iSGLT2 induced glycosuria up to 85 g/day by 24 hours and therefore in a 60 year old patient with overweight (BMI 28 kg/m²) and in a diet with 50% of carbohydrates, this glycosuria should cause a loss of 17 to 34% of carbohydrates consumed in men and 22 to 44 % in women [84]. These drugs induce insulin release and decrease of glucagon routinely, but in those patients with a strict glucose control, the persistent action of iSGLT2 could decrease insulin release due to a decrease in glucose (main effector). This hormonal change releases the inhibition of gluconeogenesis in the liver causing moderate fasting and postprandial hyperglycemia (glucose remain being eliminated by the kidneys), and subsequently stimulates lipolysis with an increase on serum free fatty acids (up to 40%) and lipid oxidation (up to 20%) [85]. Free fatty acids released are transported to the liver where β -oxidation increases with formation of ketone bodies. Finally, iSGLT2 also induces volume depletion, which aggravates that condition. Furthermore, it seems that reported cases were associated with special conditions where patients decreased insulin doses due to iSGLT2 effect on serum glucose, but there were increased requirements (such as stress, infections or use of alcohol).

Further studies are needed to determine conclusively if ketoacidosis depends on type of drug used (which in turn depends on variability of the inhibition's degree of SGLT2 between drugs) and if their existence restricts the widespread use of these drugs.

8. PATIENTS, MATERIAL AND METHODS

Type of study: Phase II/III, controlled, randomized, open clinical trial.

By study groups: two parallel groups' design.

By maneuvering: experimental

By measurements in the population: longitudinal

By temporality: prospective

By the nature of the study: clinical

By purpose: Therapeutic

Study Population

- Patients with obesity class III from the "Obesity Clinic" in preparation for bariatric surgery.
- Study period: December 2016 to October 2018
- Place of study: Mexico City, Mexico
- Time of clinical assessment of each patient: one year

Workplan

- 1) A convenience sampling will be done for patients diagnosed with diabetes or prediabetes according to ADA criteria [12] (Appendix 1), who come to Obesity Clinic in the indicated period and that meet the selection criteria. Since the first assessment, patients are informed that they would become candidate for bariatric surgery (bypass or gastric sleeve, depending on surgeons' criteria) once they achieve a weight reduction of 10%.
- 2) Due patients achieve weight loss needed for the surgical procedure at different times of follow-up (3, 6 or 12 months), clinical, biochemical, and initial and final determinations of inflammatory cytokines and hormones, will be collected until the previous valuation before surgery. Data will be collected even if the patients require treatment with sulfonylureas or insulin (adverse event grade 3).
- 3) Prevalence of comorbidities at baseline and the type and dose of drugs used for treatment will be recorded (Appendix 2. Data Collection Sheet). Treating physicians based on the clinical response of patients, will decide the dose and number of drugs and will record changes in the corresponding data sheet.
- 4) Patients will be randomized by a random numbers system generated with a computational software and will be assigned to a group: 1) metformin (2 g/day) or 2) metformin (2 g/day) and dapagliflozin 10 mg. All patients will receive dietary treatment and follow-up during the study by Nutrition service. Dietary treatment is individualized, as it is based on the initial weight of the patient and their eating habits at the time of valuation. It is expected that dietary treatment does not influence the results because all patients will undergo diet and those with little attachment (defined as failure to comply with at least 80% of the prescribed diet) are discharged of the surgical protocol. The Nutrition service calculates the percentage of adherence to diet.
- 5) Once assigned to the corresponding group, patients will receive an identification code that will be retained throughout the study. One of the researchers not directly involved in patient care, will assign tablets needed for daily intake for a month and then the number of tablets required for 3 months in a sealed envelope.
- 6) A run-in period will be used to assess tolerance to treatments. This period will be for a month. At this time patients will be advised of a possible increase on urea and will be instructed in the relevance of increasing fluid intake.
- 7) The anthropometrical and biochemical variables will be recorded at baseline and at 1, 3, 6 and 12 months (Appendix 2. Data Collection Sheet). A clinical nutritionist accredited as Level 1 Anthropometrist by the International Society for the Advancement of Kinanthropometry (ISAK) will assess the weight on a scale with a

maximum capacity of 300 kg and precision of 100 g; height using an stadiometer, and waist circumference using a fiberglass tape, according to the manual of procedures for nutrition projects of the Centro de Investigación en Nutrición y Salud de Instituto Nacional de Salud Pública [86], and also in accordance with the procedures manual for the assessment of clinical and anthropometrical measurements in the adult and elderly of the Ministry of Health [87] (Appendix 3. Clinical and anthropometric measurements).

- 8) The determination of blood pressure will be performed by a nurse from the Obesity Clinic, using an aneroid sphygmomanometer, recording the average of two measurements taken with a 5-minutes difference, according to the procedure's manual for the assessment of clinical and anthropometrical measurements in the adult and elderly of the Ministry of Health (Appendix 3. takes clinical and anthropometric measurements).
- 9) The determination of insulin, glucagon, ghrelin, adiponectin, resistin, IL-6, IL-10 and TNF- α will be held at baseline and before surgery (depending on the response of each patient). For the determination of these cytokines and peptides, an ELISA kit (enzyme linked immunosorbent assay) will be used (Appendix 4. ELISA technique).
- 10) Adherence to treatment will be evaluated and will consist in consumption of 90% of pills granted. The registration of adverse events will take place from the start of treatment and throughout the study. Each event will be evaluated by researchers and classified according to CTCAE list (Common terminology criteria for adverse events version 4.03). CTCAE considers that an adverse event grade 4 or 5 indicates discontinuation of treatment; grade 3 must be submitted to review by the medical team, and grades 1 or 2 require registration and intervention but not discontinuation of treatment (Appendix 5. CTCAE list). Adverse events will be recorded in the report sheet (Appendix 6. Sheet report for drug side effects).
- 11) The patients that do not achieve weight loss at one-year follow-up will be discarded to their primary care hospital as pre-specified by the Obesity Clinic internal regulation.

Selection criteria

Inclusion criteria

- 1. Age from 18 to 60 years
- 2. Any gender
- 3. BMI greater than or equal to 40 kg/m²
- 4. Diagnosis of diabetes or prediabetes according to the criteria of the ADA. Patients must have glycated hemoglobin less than 9%.
- 5. Patients who sign informed consent letter (Appendix 7. Charter informed consent)
- 6. Candidates to bariatric surgery

Exclusion criteria

- 1. Current use of insulin or sulfonylureas
- 2. Chronic kidney disease with glomerular filtration rate <60 ml/min/1.73 m²
- 3. Use of loop diuretics with no possibility to suspend.

4. Concomitant illnesses that predispose to volume depletion, weight loss (including oncological diseases), or metabolic acidosis (including drug users)
5. History of recurrent genital or urinary tract infections
6. Use of drugs for weight control.
7. Untreated or uncontrolled hypothyroidism (defined through TSH higher than 4.2 μ U/ml)
8. Pregnant or lactating mother.
9. Tobacco use (in the last month)
10. Current use of steroids or nonsteroidal anti-inflammatory drugs

Withdrawal criteria

1. Becoming pregnant during the study
2. Tobacco use
3. Use of steroids during the study

Sample size

Weight loss after dapagliflozin treatment has not been previously used as primary outcome in randomized controlled trials (RCT) of patients with prediabetes or diabetes and grade III obesity. Zhang et al. performed a meta-analysis that included seven RCTs evaluating the effect of metformin combined with SGLT2-inhibitors (dapagliflozin 10 mg/day, canagliflozin 300 mg/day, empagliflozin 25 mg/day, or ipragliflozin 300 mg/day) vs. metformin (at doses of 1.5 to 3 g/day) with placebo on HbA1c; fasting plasma glucose; and body weight over 24 weeks, 1 year, and 2 years. The total sample was 2847 patients with a mean BMI of 31.7 ± 4.9 kg/m². After a year of treatment, the placebo-metformin control group showed a reduction in body weight of 1.1 ± 3.39 kg, whereas the SGLT-2 inhibitor-metformin group showed a 3.6 ± 4.22 kg reduction with a mean difference of -2.6 kg (-3.17 to -2.03 kg), $p < 0.0000$. Using these data, we calculated a sample size using a mean difference formula. With a power of 80% (alpha level of 0.05) in a two-sided T-test, the sample size required is 90 patients: 45 patients in the M group and 45 patients in the D/M group. The final sample size required is 108 patients: 54 patients in metformin and 54 patients in the dapagliflozin group, allowing for a 20% dropout rate.

Variable definition

Variable name	Variable Type	Scale	Conceptual definition	Operational definition	Units
INDEPENDENT VARIABLES					

Type of treatment	Qualitative, dichotomic	Nominal	Metformin is a biguanide with effect in cyclic AMP kinase that diminishes insulin resistance. Diabetes treatment guidelines consider it as the first line therapy. Dapagliflozin is an SGLT2 inhibitor that induces glycosuria and has been approved for monotherapy in patients with metformin intolerance and also as a second or third line therapy for diabetes.	Use of metformin 2 grams per day or use of metformin 2 grams per day in combination with 10 mg of dapagliflozin.	0 = metformin, 1 = metformin/dapagliflozin
-------------------	-------------------------	---------	--	--	---

DEMOGRAPHIC VARIABLES

Age	Quantitative, continuous	Ratio	Time elapsed from birth to	Time elapsed from birth to the baseline registry of the patient.	years
-----	--------------------------	-------	----------------------------	--	-------

			the current date.		
Gender	Qualitative, dichotomic	Nominal	Taxon that gathers members of the same species.	Gender assigned in the registry documents.	0 = female 1 = male
Height	Quantitative, continuous	Ratio	Length of a human body when measured in a standing position from the top of head to the floor.	Height registered in the baseline documents using the same stadiometer in all patients during the first evaluation.	meters (m)
Body mass index (BMI)	Quantitative continuous	Ratio	Measurement that associates height and size in the same individual and classifies them as underweight, normal, overweight or obese.	Ratio between weight in kilograms (kg) divided by the square of the height in meters. Calculation is performed in every clinical evaluation during the protocol.	kg/m²
DEPENDENT VARIABLES					
Weight	Quantitative continuous	Ratio	The force that gravitation exerts upon a body.	Total amount of kilograms registered in the same person using the same calibrated scale at baseline and months 3, 6 and 12.	kilograms (kg)

Waist circumference (WC)	Quantitative continuous	Ratio	Measurement of the body circumference measured at the minimum circumference between the iliac crest and the rib cage.	Perimeter registered in the documents using the same flexible tape at baseline and months 3, 6 and 12.	centimeters (cm)
Fasting Glucose	Quantitative continuous	Ratio	Glucose concentration in the blood serum after an 8 hour fast.	Blood glucose reported at baseline, months 3,6 and 12.	mg/dl
Fasting Insulin	Quantitative continuous	Ratio	Insulin concentration in the patients serum determined by radioimmunoassay after an 8 hour fast.	Blood insulin reported at baseline and months 3,6 and 12.	mU/L
HOMA-IR	Quantitative continuous	Ratio	The homeostatic model assessment (HOMA) is a method used to quantify insulin resistance and beta-	HOMA = [glucose (mg/dl)/18 *insulin (mU/L)]/22.5 at baseline and months 3,6 and 12.	Dimensionless

			cell function.		
Glycated hemoglobin (HbA1c)	Quantitative continuous	Ratio	Is the most abundant of the minor component s in hemoglobin , formed by the condensati on of glucose in the N-terminal portion of the beta chain of the hemoglobin molecule, representin g an average of blood glucose concentrati on for the last three months.	Percentage of glycated hemoglobin in the blood of patients at baseline and months 3,6 and 12, using immunoanalysis with turbidimetric inhibition.	%
Cholesterol	Quantitative continuous	Ratio	Total cholesterol in the serum of the patient after an 8-12 hour fast.	Magnitude obtained in lipid profile of patients at baseline and months 3,6 and 12 after an 8-12 hour fast.	mg/dl

Triglycerides	Quantitative continuous	Ratio	Triglyceride concentration in the serum of the patient.	Magnitude obtained in lipid profile of patients at baseline and months 3,6 and 12 after an 8-12 hour fast.	mg/dl
c-HDL	Quantitative continuous	Ratio	High-density cholesterol concentration in the serum of the patient.	Magnitude obtained in lipid profile of patients at baseline and months 3,6 and 12 after an 8-12 hour fast.	mg/dl
c-LDL	Quantitative continuous	Ratio	Low-density cholesterol concentration in the serum of the patient calculated using the Friedwald formula.	c-LDL = total cholesterol - (c-HDL + triglycerides/5) at baseline and months 3,6 and 12 after an 8-12 hour fast.	mg/dl
Systolic and diastolic blood pressure	Qualitative nominal	Nominal Dichotomic	Measurement of the pressure of the blood against the inner walls of the blood vessels.	Blood pressure determined by the same investigator in two different measurements after 30 minutes of resting in a sitting position, performed 5 minutes apart from each other.	mmHg
Adiponectin	Quantitative continuous	Ratio	Protein secreted exclusively by the adipose tissue and directly related to	Concentration determined using the method ELISA.	pg/ml

			insulin resistance.		
Resistin	Quantitative continuous	Ratio	Protein, member of the RELM family, related to insulin resistance in the liver tissue.	Concentration determined by using the method ELISA.	ng/ml
Interleukine 6 (IL-6)	Quantitative continuous	Ratio	Pro-inflammatory cytokine, secreted by adipose tissue and related to insulin resistance mediated by the insulin receptor.	Concentration determined using the method ELISA.	pg/ml
Interleukine 10 (IL-10)	Quantitative continuous	Ratio	Anti-inflammatory cytokine related to the development of atherosclerosis	Concentration determined using the method ELISA.	pg/ml
Ghrelin	Quantitative continuous	Ratio	Hormone secreted in the gastric fundus that induces appetite.	Concentration determined using the method ELISA.	pg/ml

Glucagon	Quantitative continuous	Ratio	Hormone produced by pancreatic alpha cells that counteracts the effects of insulin.	Concentration determined using the method ELISA.	ng/ml
----------	-------------------------	-------	---	--	-------

Statistical analysis: Quantitative variables were described using measures of central tendency and dispersion according to the data distributions. Qualitative variables were described using frequencies or percentages. The Shapiro-Wilk test was used to establish normality in the distribution of quantitative variables. Because information on the different quantitative variables was available up to different time periods, a mixed model analysis was performed using the restricted maximum likelihood (REML) method, as well as a mixed model considering the fixed effects of assigned treatment, sex, and prediabetes or diabetes status, and the random effects of variability in weight loss over time. Comparisons between groups were analyzed using Sidak's post-hoc test. Pearson's chi-square test or Fisher's exact test were used to evaluate the association between qualitative variables. Statistical significance was defined as a $p < 0.05$. Data analysis was performed using SPSS version 17.0 and STATA version 11.0.

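### No stated procedure keeps the arm from the staff who measure waist and blood pressure or score diet adherence in this open trial; masking them is a cheap improvement

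*Combined protocol and SAP*

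**What the plan says.** Section 8 (Type of study) calls the trial a "Phase II/III, controlled, randomized, open clinical trial". Workplan item 4 gives the arms as "1) metformin (2 g/day) or 2) metformin (2 g/day) and dapagliflozin 10 mg"; no placebo is described.

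The tasks are divided as follows in Section 8:

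- **Prescribing** (Workplan item 3): "Treating physicians based on the clinical response of patients, will decide the dose and number of drugs".
- **Dispensing** (Workplan item 5): "patients will receive an identification code that will be retained throughout the study", and "One of the researchers not directly involved in patient care, will assign tablets needed for daily intake for a month", followed by a three-month supply in a sealed envelope.
- **Weight and waist** (Workplan item 7): an accredited clinical nutritionist.
- **Blood pressure** (Workplan item 8): "The determination of blood pressure will be performed by a nurse from the Obesity Clinic, using an aneroid sphygmomanometer". The variable table differs: "Blood pressure determined by the same investigator in two different measurements".
- **Diet adherence** (Workplan item 4): "The Nutrition service calculates the percentage of adherence to diet". Patients below 80% are discharged from the surgical protocol.

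The Appendix 2 data sheet has a treatment-code field in its header. Its follow-up table holds weight, waist and blood pressure together with a row for drugs, including hypoglycemic agents.

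**The concern.** Waist and blood pressure are named in the primary objective (Section 6). The hypothesis (Section 5) states the direction expected in each arm: a 5% fall with the combination and no effect with metformin alone. A tape reading and an aneroid reading both leave room for judgement, and Appendix 3 itself concedes that waist is hard to assess in very obese people, which describes everyone enrolled. An observer who knows the arm and the hypothesis can shift readings without intending to. Unlike random error, a shift of this kind does not average out with more patients.

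The diet score raises a second issue. Workplan item 4 argues that diet will not affect the results partly because poorly adherent patients leave the surgical protocol. If the scorers know the arm, that safeguard is itself open to influence.

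**Working it through.** **Does anything already mask the assessors?** The plan states no figure on this point, so the check is a reading of the text.

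1. The code, the outside-care tablet assignment and the sealed envelope appear together in Workplan item 5. They govern how tablets reach patients. None is described as withholding the arm from those who measure.
2. Appendix 2 works against masking. The plan does not say whether the treatment code is neutral (the variable table codes the arms 0 and 1), but a list of current hypoglycemic drugs on the same form would show the arm to whoever completes it.
3. Under the Workplan, the people who measure are not the people who prescribe. For blood pressure this holds only if item 8 (nurse) prevails over the variable table (investigator).
4. The blood-pressure procedure also varies. The variable table has 30 minutes of rest and readings 5 minutes apart; Appendix 3 has at least 5 minutes of rest and readings two minutes or more apart. This adds to the observer's discretion.

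**How large might a bias be against the cited effects?** Section 7 cites 1.52 cm for waist, 3.78 mmHg systolic and 1.41 mmHg diastolic. The shifts below are assumptions. Share = shift / effect.

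| Assumed shift | Waist | Systolic | Diastolic |
|---|---|---|---|
| 0.5 cm or 1 mmHg | 0.5/1.52 = 33% | 1/3.78 = 26% | 1/1.41 = 71% |
| 1 cm or 2 mmHg | 1/1.52 = 66% | 2/3.78 = 53% | 2/1.41 = 142% |

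The abstract also quotes 4 to 5 mmHg systolic, for which a 2 mmHg shift is 2/5 = 40% to 2/4 = 50%.

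**Against the plan's own hypothesis.** A 5% fall exceeds the cited effect whenever baseline is above 1.52/0.05 = 30.4 cm, 3.78/0.05 = 75.6 mmHg or 1.41/0.05 = 28.2 mmHg, so the shares are smaller on this scale. With assumed baselines of 120 cm and 130 mmHg systolic, the targets are 6 cm and 6.5 mmHg, and the shares are 1/6 = 17% and 2/6.5 = 31%.

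**Effect on the error rate.** The planned size is first reproduced, using the crude difference 3.6 − 1.1 = 2.5 kg and the larger SD of 4.22 kg:

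n per arm = 2 × (1.960 + 0.842)² × 4.22² / 2.5² = 44.7, rounded up to 45, as stated.

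The plan gives no SD for waist or blood pressure, so the shift b is in SD units. With 45 per arm and no true effect, SE = √(2/45) = 0.211, and the two-sided 5% false-positive rate is 1 − Φ(1.96 − b/SE) + Φ(−1.96 − b/SE):

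- b = 0.1: 7.6%
- b = 0.2: 15.8%
- b = 0.3: 29.6%

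This is a simple two-group comparison, not the planned mixed model, and it illustrates scale only.

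**The case against.** The open design is declared, and without a placebo patients know their treatment, so masking could never be complete. The protocol already limits observer discretion: an accredited anthropometrist, written manuals, a second person to check the tape, and averaged blood-pressure readings with two more when the first pair differ by over 5 mmHg. The sample size rests on body weight alone, read from a scale calibrated monthly. The shifts used above have no source in the documents, and the cited effects come from patients with BMI under 40.

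Most of this stands, and it limits the point without removing it. Standardised technique reduces random error and some discretion, but it does not stop a reader who knows the arm from leaning one way. An open treatment design does not prevent masked measurement.

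Three stronger readings are tempting, and the documents do not support them:

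- **That nothing limits knowledge of the arm.** Workplan item 5 does contain limiting steps; they stop at dispensing.
- **That arm-aware diet scoring will bias who remains in the trial.** Discharge is from the surgical protocol. The plan does not say that it ends trial follow-up, and the withdrawal criteria list only pregnancy, tobacco and steroids. Selection bias is a risk, not a certainty.
- **That masking would be free.** The shared data sheet must be separated, and patients may still reveal their arm.

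**Conclusion.** The point holds as a worthwhile, inexpensive improvement. The plan states no masking for the assessors of two outcomes named in the primary objective, or for the scorers of diet adherence, and its own data sheet exposes the arm to them. The Workplan already gives these tasks to staff who do not prescribe, subject to resolving who takes blood pressure.

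The size of any bias is unknown. Under the assumed shifts of 0.5 to 1 cm and 1 to 2 mmHg, it would be 33% to 66% of the cited waist effect, 26% to 53% of the systolic effect and 71% to 142% of the diastolic effect, with smaller shares of the hypothesised 5% reductions. These figures show that a modest shift could matter; they are not evidence that one will occur. A reader might infer that the weight comparison is compromised as well. The documents do not support that: weight is read from a calibrated scale and is less exposed to reading bias.

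**What to change.** 1. State in Section 8 that the anthropometrist, the blood-pressure nurse, the nutritionist scoring diet adherence and the ELISA laboratory work from the patient code and are not told the arm.
2. Split Appendix 2. Put the treatment code and the drug row on a separate form completed by the treating physician, and leave the measurement form with the patient code only.
3. Ask patients not to disclose their tablets to assessors. Treatment counselling stays with the treating physicians.
4. Reconcile Workplan item 8 with the variable table so that blood pressure is taken by someone masked to the arm, and align the rest and interval times with Appendix 3 in the same edit.
5. State whether discharge from the surgical protocol for poor diet adherence ends trial follow-up.

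The cost is protocol wording, a second form and a short instruction to patients. No extra assessor or placebo is needed, and no sample-size input changes, so 45 per arm stands. The limitation is partial masking, because patients know their treatment.

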Primary objective: To determine if combined treatment with dapagliflozin and metformin is more effective than monotherapy with metformin for weight loss and assess its effects on waist circumference, triglycerides, blood pressure and inflammatory cytokines (resistin, adiponectin, interleukin-6 and interleukin-10) in prediabetic and diabetic patients with obesity class III.

Secondary objective: To determine the effect of combined treatment with dapagliflozin and metformin in comparison with monotherapy with metformin on serum concentrations of glucagon, ghrelin and insulin.

Patients, material and methods: The protocol includes patients with previous or recently diagnosed diabetes or prediabetes from the Obesity Clinic of CMN SXXI from July 2018 to August 2023 age 18 to 60 years old, both male or female and not treated with insulin. Patients requiring initial treatment with insulin, with obesity secondary to other comorbidities and patients who do not wish to enter the study or not provide their informed consent will be excluded. Patient's data that during the study are advised to undergo bariatric surgery will be used until the moment of surgery. Other treatments will be adequately recorded. Patients will be randomized by computer software and assigned in a group treated with metformin (>2 g/day, group 1) or with metformin (>2 g/day) and dapagliflozin 10 mg (group 2). All patients will receive dietary treatment and follow-up by the Nutrition service during the study. Anthropometric and biochemical variables will be recorded at the beginning and at months 3, 6 and 12. Adherence to treatment will be assessed, defined by consumption of at least 90% of provided pills. The adverse events will be recorded since the beginning of study and will be ranked according to the CTCAE lists (Common terminology criteria for adverse events version 4.03). An intention-to-treat analysis will be performed in case of patients that require treatment with insulin.

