5. HYPOTHESIS

Dapagliflozin in combination with metformin induce 10% of weight lost and 5% of decrease in waist circumference, triacylglycerol concentration, blood pressure and inflammatory cytokines in patients with prediabetes or diabetes with class III obesity, in comparison with the 5% of weight lost and lack of effect in the rest of parameters in patients treated with metformin monotherapy.

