6. OBJECTIVES

- a. **Primary objective:** To determine if combined treatment with dapagliflozin and metformin is more effective than monotherapy with metformin for weight loss and assess its effects on waist circumference, triglycerides, blood pressure and inflammatory cytokines in patients with prediabetes and diabetes with obesity class III.
- b. **Secondary objectives:**
 - i. To determine efficacy of metformin monotherapy for weight loss and decrease on waist circumference, triglycerides and blood pressure in patients with prediabetes and diabetes with obesity class III.
 - ii. To compare efficacy of metformin monotherapy and combined treatment with metformin and dapagliflozin.
 - iii. To determine the percentage of patients that with combined treatment achieves a decrease in total weight of 5%, 10% and 15% and the percentage of patients that achieve a decrease in 10% of excess weight.
 - iv. To evaluate if combined treatment allows a decrease in number of drugs needed for comorbidities' control.
 - v. To evaluate prevalence of adverse effects commonly associated with dapagliflozin use (urinary and genital tract infections, hydroelectrolytic alterations) in patients with obesity class III.
 - vi. To determine serum concentration of adiponectin, resistin, IL-6, IL-10 and TNF- α before and after treatments, and compare it between groups.
 - viii. To determine serum concentration of insulin, glucagon and ghrelin before and after treatments, and compare it between groups.

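### The end of adverse-event collection for patients who go to surgery is inconsistent; if it stops at or before surgery, observation time depends on weight response and the planned crude prevalence can understate a dapagliflozin excess

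*Combined protocol and SAP*

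**What the plan says.** Three places in the combined protocol and SAP bear on when adverse-event collection ends.

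- Section 8, Workplan item 2: patients reach the weight loss needed for surgery at month 3, 6 or 12, and clinical and biochemical data, with the cytokine and hormone determinations, "will be collected until the previous valuation before surgery". Adverse events are not named.
- Section 2, Abstract: "Patient's data that during the study are advised to undergo bariatric surgery will be used until the moment of surgery".
- Section 8, Workplan item 10: adverse events are registered from the start of treatment for as long as the study lasts. Section 8 also sets one year of assessment per patient, but does not say whether that year continues after an operation.

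Objective v (section 6) is "To evaluate prevalence of adverse effects commonly associated with dapagliflozin use (urinary and genital tract infections, hydroelectrolytic alterations)". Several of its components (urinary infection, leukocyturia, nitrite, sodium, potassium) are fields on the visit sheet in Appendix 2. Other events go on the form in Appendix 6.

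The Statistical analysis paragraph recognises that follow-up differs between patients and answers this with a mixed model for quantitative variables only. Qualitative variables are given as frequencies or percentages and compared by chi-square or Fisher's exact test. No person-time or time-to-event analysis is planned.

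The hypothesis (section 5) is "Dapagliflozin in combination with metformin induce 10% of weight lost", against 5% on metformin alone. Workplan item 1 makes a patient a surgical candidate after a 10% weight reduction. The Background's description of the Obesity Clinic gives the threshold as 10% of excess weight.

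**The concern.** On the Workplan item 2 or Abstract reading, the length of safety observation is a consequence of treatment response. If the trial's hypothesis is right, more dapagliflozin patients leave at month 3 or 6, and each early leaver has less time in which an infection can be recorded. A crude percentage divides events by patients, not by time watched, so the shorter-observed arm looks safer than it is. The plan allows for unequal follow-up in its quantitative outcomes but not in its safety comparison.

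At stake is objective v: whether the infections already associated with the drug are more frequent in class III obesity, a population in which, according to the Background, it has not been studied.

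**Working it through.** **The plan's own figure.** No calculation is given for adverse events. The only design calculation is the sample size: "With a power of 80% (alpha level of 0.05) in a two-sided T-test", from a control arm that "showed a reduction in body weight of 1.1 ± 3.39 kg" and an SGLT2-inhibitor arm that "showed a 3.6 ± 4.22 kg reduction". With a difference of 3.6 − 1.1 = 2.5 kg and the larger SD, n = 2 × (1.960 + 0.842)² × 4.22² / 2.5² = 44.7, so 45 per arm, as stated. It matters here only as a second source of expected weight losses.

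**Inputs from the documents.** Odds ratios of 1.43 (urinary) and 3.48 (genital) from the Background; losses of 10% against 5% from section 5; exits possible at months 3, 6 or 12.

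**Assumptions, not in the documents.** One-year control risk of 20% urinary and 5% genital; constant event rates; normally distributed weight loss with SD 5 points (4 to 7 as a range); the exit patterns below; everyone who meets the trigger is operated on.

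**Formulas.** With one-year risk p, λ = −ln(1 − p). Observed risk = Σ wₜ(1 − e^(−λt)), where wₜ is the share whose observation ends at time t (years).

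Urinary: control λ = −ln 0.80 = 0.223. Dapagliflozin odds = 0.25 × 1.43 = 0.3575, so p = 0.3575/1.3575 = 26.3% and λ = 0.306.

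**Worked case (row 5).** Half the combined arm exceeds 10%, since that is the hypothesised mean. In the metformin arm 1 − Φ((10 − 5)/5) = 15.9% do. Leavers are split equally between months 3 and 6.

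- Dapagliflozin: 0.25 × 0.0736 + 0.25 × 0.1418 + 0.5 × 0.2634 = 18.55%
- Metformin: 0.0793 × 0.0543 + 0.0793 × 0.1056 + 0.8413 × 0.20 = 18.09%
- Odds ratio: (0.1855/0.8145)/(0.1809/0.8191) = 1.03

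**All cases** (dapagliflozin first, metformin second). Unless stated, patients leave when the trigger is met. In rows 1 to 3 and 6, half the year's loss is reached by month 3 and 75% by month 6.

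| Case | Left at month 3, month 6 | Mean months observed | Observed urinary risk | Urinary OR | Genital OR |
|---|---|---|---|---|---|
| 1. Sample-size losses, 10% total weight (11.5 kg) | 0, 0.3%; 0, 0 | 12.0; 12.0 | 26.3%; 20.0% | 1.43 | 3.5 |
| 2. Sample-size losses, 10% excess weight (4.3 kg) | 11.8%, 18.9%; 1.3%, 7.2% | 9.8; 11.4 | 21.8%; 19.1% | 1.18 | 2.9 |
| 3. Hypothesis, 10% total weight, SD 5 | 2.3%, 23.0%; 0.1%, 4.6% | 10.4; 11.7 | 23.1%; 19.5% | 1.24 | 3.0 |
| 4. Hypothesis, leavers spread equally over 3, 6, 12 | 16.7%, 16.7%; 5.3%, 5.3% | 9.5; 11.2 | 21.1%; 18.7% | 1.16 | 2.9 |
| 5. Hypothesis, leavers split over 3 and 6 | 25%, 25%; 7.9%, 7.9% | 8.3; 10.8 | 18.6%; 18.1% | 1.03 | 2.6 |
| 6. Hypothesis, 10% excess weight, SD 5 | 69.1%, 15.0%; 30.9%, 19.1% | 4.9; 8.1 | 11.4%; 13.7% | 0.81 | 2.0 |

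Row 6 takes BMI 40 and a reference BMI of 25, so 10% of excess weight is 0.10 × (40 − 25)/40 = 3.75% of total weight.

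**Sensitivity.** Row 3 with SD 7 gives a urinary odds ratio of 1.21; adding three months between trigger and surgery gives 1.31 to 1.33. Row 5 ranges from 0.99 to 1.10 for a metformin-arm SD of 4 to 7. With control risks of 5% and 10%, row 5 gives 1.08 and 1.06, and row 6 gives a risk ratio of 0.85 in both.

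**After the fix.** Under constant rates, events per person-year give a urinary rate ratio of 0.306/0.223 = 1.37 in every row (about 1.4 at control risks of 5 to 10%), whatever the exit pattern.

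**The case against.** The strongest reply is textual. Workplan item 2 does not mention adverse events; item 10 does, and it sets no stop at surgery. If item 10 means a full year for everyone, observation is equal and the bias disappears. That stands as a possible reading. It does not settle the matter, because the Abstract's limit makes no exception for safety and several objective v items are visit-sheet fields that would end with the visits.

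The second reply concerns size. Meeting the trigger makes a patient a candidate; it is not an operation, and the documents describe about 250 patients waiting or awaiting approval. Delay shrinks the effect. The near-null urinary result of row 5 needs every leaver to exit by month 6, although month 12 is also listed. Infections concentrated in the first three months would be little affected. Discharge for poor diet adherence (item 4) could also change observation time. All of this stands, and is why a range is given.

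Third, precision is poor anyway. With 54 per arm and risks of 20% and 26.3%, the arcsine difference is 2(0.5389 − 0.4636) = 0.151. Then 0.151 × √27 = 0.78, and power is 1 − Φ(1.96 − 0.78), about 12%. Failure to detect a urinary excess would therefore mostly reflect sample size. That does not excuse a systematic shift in the estimate.

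A reader might also infer that the cut-off hides ketoacidosis around surgery. The Background describes patients who had lowered their insulin dose, "but there were increased requirements (such as stress, infections or use of alcohol)", and does not mention surgery. Current insulin users are excluded, and objective v does not name ketoacidosis. The link is inference and carries no weight here.

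**Conclusion.** The concern holds in conditional form. The documents give three incompatible or incomplete end points for an operated patient's safety data, and the planned comparison takes no account of time at risk. If collection stops at or before surgery and dapagliflozin patients respond better, the crude comparison can understate an excess.

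A reader might go further and conclude that adverse-event follow-up does end at the visit before surgery and that the trial will understate harm. The text does not support that. The cut-off sentence does not name adverse events, and the direction requires a better response on dapagliflozin, reasonably prompt surgery and events spread over the year.

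The size runs from nil (sample-size losses, total-weight trigger), through a urinary odds ratio of 1.43 seen as about 1.0 to 1.3 (hypothesis, total-weight trigger), to a ratio below 1 (hypothesis, excess-weight trigger). Control risks, SDs, exit timing and surgical delay are assumptions throughout. The unresolved conflict between the two triggers alone moves the answer from modest to large.

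**What to change.** 1. Reconcile the Abstract with Workplan items 2 and 10 into one stated adverse-event window applied to both arms, and report any post-surgery events separately because surgery itself causes events. A window that does not depend on weight response removes the problem at source.
2. Report objective v in both arms as events per person-year on treatment, or as time to first event, using dates of first tablet, last tablet, event and surgery. Percentages can stay as description.
3. Reconcile the 10% total-weight threshold (Workplan item 1) with the 10% excess-weight threshold (Background), since exit timing depends on it. Which is intended is for the investigators to state.

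The cost is protocol and SAP wording and two added date fields, last tablet and surgery, if the inclusion date in Appendix 2 can serve for the first tablet. Appendix 6 already has a date column, which should be defined as date of onset. The rate analysis assumes a roughly constant hazard; time to first event avoids that. Both still assume that leaving for surgery is unrelated to a patient's event risk within an arm, so step 1 should not be skipped.
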